## **7.0 Enrollment/Randomization**

**7.1 Study Sites:** Patients for this study will be enrolled upon admission to the participating intensive care unit (ICU) at Vanderbilt University Medical Center. Participating ICUs within Vanderbilt University Hospital will include:

**SMART-MED:** Medical ICU (8T3)

**SMART-SURG:** Surgical ICU (9T3), Cardiovascular ICU (5N), Trauma ICU (10N), Neurological and Neurosurgical ICU (6T3).

**7.2 Study Population:** All patients admitted to an ICU at Vanderbilt Medical Center during the study period will be enrolled unless meeting exclusion criteria. Patients will be enrolled prior to receiving their first administration of IV fluid in the ICU.

Principal Investigators: [name], [name]

Version Date: 6/15/17

Study Title: Isotonic Solutions and Major Adverse Renal Events Trial (SMART)

Institution/Hospital: Vanderbilt University Medical Center

**7.3 Enrollment:** All adult patients will be enrolled in this cluster-randomized, multiple-crossover trial at the time of admission to the participating ICU prior to the administration of any IV fluid in the ICU.

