## **8.4 Data Collection**

### **8.4.1 Data at Enrollment**

1. Study Enrollment Data:
  - a. Encounter Number ("Study ID")
  - b. Medical Record Number
  - c. Date and Time of ICU Admission ("Time Zero")
  - d. Study ICU at enrollment (Medical/Cardiac/Neuro/Trauma/Surgical)

Principal Investigators: [name], [name]

Version Date: 6/15/17

Study Title: Isotonic Solutions and Major Adverse Renal Events Trial (SMART)

Institution/Hospital: Vanderbilt University Medical Center

2. Demographic Data:

- a. Age (years)
- b. Gender (male/female)
- c. Race (White/Black/Asian/Alaskan/PacificIsland/Other)
- d. Ethnicity (Hispanic, Non-hispanic)
- e. Height (cm)
- f. Weight (kg)
- g. Date and time of Hospital Admission
- h. Source of admission to ICU (ED/OR/outside hospital transfer/hospital ward/outpatient/another ICU within the hospital)
- i. Admitting service
- j. ICD-9 and ICD-10 diagnoses

3. Comorbidities:

- a. Exlihauser comorbidities
- b. CKD stage III or greater by CKD-EPI criteria
- c. Prior receipt of renal replacement therapy
- d. Predicted risk of in-hospital mortality by University HealthSystem Consortium expected in-hospital mortality

4. Invasive Support:

The following information will be recorded during the 12 hours prior to and 24 hours following ICU admission (“Time Zero”). If more than one value is available for this 36-hour period, the value closest to the time of ICU admission (“Time Zero”) will be recorded.

- a. Receipt of Mechanical Ventilation (Y/N)
- b. Receipt of vasopressors (Y/N) (norepinephrine, epinephrine, dopamine, phenylephrine, or vasopressin)

5. Renal function

- a. All serum creatinine values from the clinical laboratory system between 12 months prior to hospitalization and 30 days after ICU admission
- b. Stage II or greater acute kidney injury by KDIGO creatinine criteria

6. Serum laboratory values

- a. All serum values for sodium, potassium, chloride, bicarbonate, and blood urea nitrogen between 12 months prior to hospitalization and 30 days after ICU admission

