## Population

All adults (age  $\geq 18$  years) admitted to a participating ICU at Vanderbilt University Medical Center during the study period are enrolled at the time of ICU admission. Enrolled patients who are discharged from the hospital are eligible again if they are admitted to a participating ICU again during the study period.

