Although the study focuses on crystalloid use in the ICU, crystalloid administration prior to ICU admission in the emergency department or operating room may introduce contamination and limit separation between study arms. Therefore, between January 1, 2016 and April 30, 2017, the Vanderbilt University Medical Center Emergency Department (ED) is coordinating their crystalloid use with the medical, surgical, and trauma ICUs such that patients admitted to those units from the ED begin receiving the assigned crystalloid during evaluation and management in the ED (NCT02614040). Clinical outcomes of patients treated with study crystalloids in the ED and hospitalized outside the ICU will be recorded and reported separately. Similarly, to the extent that is logistically feasible, for patients identified in the operating room as coming from or being admitted to one of the participating ICUs, the request is made that they receive the fluid assigned to the corresponding ICU during their operative

procedure. Fluid administered prior to enrollment by the emergency medical system and outside hospitals, and fluid administered after discharge from the ICU, is not controlled by the study.

Each day patients receive the crystalloid to which their ICU is currently assigned. The necessity that an intravenous crystalloid be clinically available at all times precluded the use of washout periods and patients who remain in the ICU through a crossover (i.e., from one calendar month to another) may potentially be exposed to both types of crystalloid. Although this introduces the potential for contamination of study groups, in a pilot trial at the same institution, the total volume of non-assigned crystalloid administered due to the lack of a washout period was less than 125 mL per patient[14]. As described in the *Statistical Analysis* section below, patients will be analyzed in the group to which they were assigned at the time of study enrollment in an intention-to-treat fashion (e.g., a patient admitted to an ICU during a month assigned to saline will be analyzed in the saline group even if that patient remains in the ICU after the ICU switches assignment to balanced crystalloids).

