## Primary Analysis

To account for the cluster-level-allocation, cluster-level-crossover structure of the trial, the primary analysis will be an intention-to-treat comparison of the primary outcome of MAKE30 between the saline and balanced crystalloid groups using a generalized linear mixed-effects model including fixed effects (group assignment, age, gender, race, source of admission, mechanical ventilation, vasopressor receipt, diagnosis of sepsis, and diagnosis of traumatic brain injury) and random effects (intensive care unit)[27,28].

In preparation for SMART, we electronically collected the same set of variables that would be used to analyze SMART from the records of all 11,582 patients admitted to the study ICUs between January 1, 2014 and December 31, 2014. With the data on MAKE30 from the 11,582 patients admitted in the year before the trial, using generalized linear mixed-effects modeling treating the five ICUs as clusters and the 12 months as periods, we calculated the intra-cluster correlation coefficient to be 0.142, the intra-period correlation coefficient to be 0.026, and the intra-cluster intra-period correlation coefficient to be  $<0.001$ .

Using the data from the 11,582 patients admitted in the year before the trial, we performed a series of simulated trials evaluating a variety of trial conditions and potential results including: (1) outcome differences between groups ranging from no difference to a 50% relative risk reduction, (2) heterogeneity of treatment effect by cluster, (3) change in the incidence of the outcome in the control group over the course of the trial, (4) varying levels of intra-cluster correlation, and (5) varying levels of intra-period correlation. In each case the generalized linear mixed-effect model appeared to adequately account for the correlation between participants. Analysis using generalized linear mixed-effects modeling and generalized estimating equations accounting for the same variables produced identical odds ratios and 95% confidence intervals for the difference between the simulated groups in the primary outcome.

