## Additional Secondary Analyses

We will perform the following additional secondary analyses:

- (1) Comparison of secondary outcomes between study groups.
- (2) Effect modification by severity of illness and pre-specified subgroups. Using generalized linear mixed effects modeling, we will examine the interaction between crystalloid assignment and the following baseline variables with respect to the primary outcome of MAKE30 in the intention-to-treat population:

- a. Source of admission to the ICU (Emergency department, Operating room, Transfer from another hospital, Hospital ward, Other)
- b. Study ICU (Medical, Surgical, Cardiac, Neurological, Trauma). [Because cluster cannot be treated as a random effect for this subgroup, we will use logistic regression modeling]
- c. Sepsis or septic shock (Yes, No)
- d. Traumatic brain injury (Yes, No)
- e. Receipt of mechanical ventilation (Yes, No)
- f. Receipt of vasopressors (Yes, No)
- g. Category of renal dysfunction at the time of enrollment (No renal dysfunction, Acute kidney injury, Chronic kidney disease, End-stage renal disease receiving RRT)
- h. Risk of in-hospital mortality as predicted by baseline University HealthSystem Consortium expected in-hospital mortality (continuous variable ranging 0.0 to 1.0)

(3) Sensitivity analysis excluding patients admitted in the week prior to a crossover ('washout'). We will repeat the primary analysis comparing MAKE30 between study groups in the intention to treat population excluding those admitted in the 7 days prior to a crossover in ICU crystalloid assignment (simulating a "washout" period). Prior data from the study ICUs suggests that less than 10% of patients remain in the ICU for longer than 7 days[14]. Excluding those admitted within 7 days of a crossover in ICU crystalloid assignment will allow use of a baseline factor to exclude the majority of patients who would go on to experience a crossover in crystalloid assignment due to the study design.

(4) Sensitivity analysis excluding patients who were transferred between ICUs or remained in the ICU through a crossover ('per protocol'). We will repeat the primary analysis comparing MAKE30 between study groups in the intention to treat population excluding those who remained in the intensive care unit through a crossover in crystalloid assignment or were transferred between study ICUs.

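### In the documents supplied, the only coding rule for mechanical ventilation and vasopressor receipt, which are used as baseline covariates and subgroups, admits values from up to 24 hours after enrollment

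*Combined protocol and SAP*

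**What the plan says.** **The rule.** Protocol (6/15/17) section 8.4.1, item 4, Invasive Support, covers two Y/N items: receipt of mechanical ventilation and receipt of vasopressors. They are "recorded during the 12 hours prior to and 24 hours following ICU admission". The tie-break reads "If more than one value is available for this 36-hour period, the value closest to the time of ICU admission". It does not prefer values before admission to values after it.

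**Enrollment.** Protocol 7.3 enrolls patients "at the time of admission to the participating ICU prior to the administration of any IV fluid in the ICU". The SAP, under Population, says that they "are enrolled at the time of ICU admission". Time Zero is therefore the moment of enrollment.

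**Use.** The SAP's Primary Analysis lists among the fixed effects "source of admission, mechanical ventilation, vasopressor receipt, diagnosis of sepsis". Under Additional Secondary Analyses (2), "we will examine the interaction between crystalloid assignment and the following baseline variables"; ventilation is item (e) and vasopressors item (f). Neither section gives a time window.

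**Intent.** The SAP's Table 1 shell lists both items as baseline characteristics. The SPIRIT figure in the published SAP places baseline variables in the enrollment column and tracks invasive support separately from ICU admission onward. Appendix 2 defines ventilator-free and vasopressor-free days but not the enrollment covariates.

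**The concern.** A covariate measured after assignment can carry part of the treatment effect. If fluid type changes how often vasopressors or ventilation are started in the first day, and some of those starts are coded Yes, the primary model adjusts away (or adds to) part of the fluid's effect. Subgroups (e) and (f) would then also be defined partly by a consequence of treatment.

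Three features of the plan make the window worth closing:

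- The SAP Discussion says that most fluid is given in the emergency department and the first 12 ICU hours, so the post-enrollment part of the window covers peak exposure.
- Protocol section 10 lists receipt of ventilation and of vasopressors among the events recorded as study outcomes, so a first-day start could count both as an outcome and as a baseline covariate.
- The fallback value for baseline creatinine stops at ICU admission; these two covariates have no such limit.

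The rule also leaves open what the nearest value of a Y/N receipt is. If charted absence of support counts as a value, most later starts are coded No. If only positive administrations count, a later start may be the only value in the window and is coded Yes.

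**Working it through.** **1. Window.** 12 h + 24 h = 36 h, as the protocol states. Of these, 24/36 = 67% fall after enrollment. This is a share of the window, not of patients.

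**2. The plan's power.** With 7,000 per group and a two-sided test at 0.05, 15.0% against 13.1% gives 89.9% power (total N for 90%: 14,056). If 15% is read as the overall rate (15.95% against 14.05%), power is 88.3%. The stated 90% is reproduced, and this point does not change it.

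**3. Illustration for vasopressors.** The documents give no figure for the bias.

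- From the documents: 14,000 patients, 15% MAKE30, 1.9-point difference.
- Assumed: 17% on vasopressors on arrival; 5% starting later under saline; vasopressor log odds ratio 1.2; balanced fluid cuts or raises later starts by 12% (5.0% × 0.12 = 0.6 points); a fraction *f* of later starts coded Yes.

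Outcome model: logit P(MAKE30) = α_g + 1.2·V, where V = 1 for support on arrival or started later, and α_g is solved so that the groups have 15.0% and 13.1%. Fitted model: logit P = β0 + β·group + γ·C, where C = 1 for support on arrival plus a fraction *f* of later starts. It is fitted to expected counts, without simulation. Power = Φ(|β|/SE − 1.96).

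With arrival-only coding, β = −0.1626 and SE = 0.0495, so 0.1626/0.0495 − 1.96 = 1.325 and power is 90.7%. In the raise scenario the arrival-only value is −0.1625.

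| Later starts coded Yes | β, 12% cut (power) | β, 12% rise (power) | β, no fluid effect on starts |
|---|---|---|---|
| 5% | −0.1623 (90.6%) | −0.1630 (90.9%) | −0.1626 |
| 10% | −0.1619 (90.5%) | −0.1635 (91.0%) | −0.1627 |
| 25% | −0.1609 (90.1%) | −0.1651 (91.5%) | −0.1630 |
| 100% | −0.1555 (87.8%) | −0.1734 (93.6%) | −0.1645 |

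Against arrival-only coding, the first three rows are 0.2%, 0.4% and 1.0% smaller with a cut, and 0.3%, 0.6% and 1.6% larger with a rise. The last row is about 4% smaller (1 − 0.1555/0.1626 = 4.4%) or about 7% larger (0.1734/0.1625 − 1 = 6.7%).

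The right-hand column moves slightly although fluid has no effect on starts. That is non-collapsibility, not bias. Measured against that column, the rises for 5%, 10% and 25% are 0.2%, 0.5% and 1.3%.

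**4. Range.** For *f* of 5% to 25%, vasopressor log odds ratio 0.4 to 1.6 and later starts of 3% to 8%, a 12% cut gives 0.04% to 2.0% smaller and at most 1.3 points of power lost. A 12% rise gives 0.05% to 3.4% larger.

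**5. Side effects of a change.**

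- If 10% or 20% of patients on support at arrival were coded No, β would move from −0.1625 to −0.1619 or −0.1613, and power from 90.7% to 90.6% or 90.5%.
- Dropping the vasopressor term altogether gives β = −0.1575 and 89.8% power, a move of about 3% (1 − 0.1575/0.1625).

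Ventilation, sepsis, admission source and ICU are not modelled. The vasopressor coefficient conditional on those is plausibly smaller, hence the lower limit of 0.4.

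**The case against.** **The deciding source was not supplied.** The SAP points to complete R code and to a supplementary file on data extraction and model development. Either may already fix these variables at arrival. This stands: the point concerns the written rule, not the coding actually used. If the code does use status at arrival, the remedy shrinks to a sentence of SAP wording.

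**Baseline intent is clear.** Table 1 and the SPIRIT figure favor reading the window as a charting tolerance. A patient charted as unsupported on arrival who starts a vasopressor at hour 10 would be coded No. This stands as to intent and limits the size, but neither source sets a window.

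**The effect may not exist.** Support for a fluid effect on early starts is thin: animal data on hypotension (protocol 2.3), nothing on ventilation, and two pilot trials without a difference in any patient outcome, though too small to exclude small ones (SAP Introduction). This stands; the illustration assumes an effect rather than showing one.

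**The crystalloid-volume analysis is a poor comparison.** The SAP adds sensitivity analyses for 30-day volume because it emerges after enrollment. A status tied to the value nearest admission is a different kind of variable. This is fair, and the point does not need the comparison.

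**Subgroups.** Analyses (e) and (f) are declared hypothesis-generating, and their bias is not quantified here. Both are true.

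**Readers can check later.** The plan promises code and de-identified data. However, analyses outside the SAP are labelled post hoc, so a pre-specified definition is worth more.

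**Conclusion.** The point holds as a cheap improvement. As written, the plan permits post-enrollment values of two primary-model covariates that it calls baseline, and nothing in the supplied SAP narrows the window.

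The bias is nil if fluid type does not affect early starts, and its direction is unknown. Under the stated assumptions it is about 0.2% to 1.6% of the log odds ratio when status on arrival is charted and 5% to 25% of later starts are coded Yes. If every later start is coded Yes, it is about 4% smaller or 7% larger, part of the latter being non-collapsibility.

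A reader might infer that the model adjusts for any support within 24 hours. With 30% having the covariate, an odds ratio of 3 to 6 and a fall of 0.5 to 2 points, that reading gives a 4% to 25% loss of log odds ratio. The documents do not support it, because the nearest-value rule excludes most later starts when arrival status is charted. Nor do they support a claim that the primary result is biased, or that the analysis code uses this window.

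**What to change.** In the SAP, define both covariates, and subgroups (e) and (f), by the last status recorded from 12 hours before ICU admission up to admission. Treat support already running on arrival as present if it is first charted within a short stated allowance (for example 1 hour); otherwise code No. Keep the 36-hour version as a sensitivity analysis.

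The cost is SAP wording, a changed time filter on the record extract and one extra run. Slightly less severity is explained, and some outside-hospital transfers already on support may be coded No because the data come from this institution's record. In the illustration (10% or 20% so coded) that costs about 0.1 to 0.2 points of power. The shift is similar in size to the smaller biases above, but it comes from weaker adjustment and not from conditioning on a post-enrollment variable.

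The change brings the covariates close to baseline, not fully there. From January 2016, "patients admitted to those units from the ED begin receiving the assigned crystalloid during evaluation and management in the ED" (medical, surgical and trauma ICUs), and for operating-room patients, where feasible, "the request is made that they receive the fluid assigned to the corresponding ICU", so status on arrival can still follow assigned fluid. A run without both covariates is optional. It does not diagnose this problem, because dropping vasopressors alone moves the log odds ratio by about 3%, more than most of the shifts in question.

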**8.4.2 Daily Study Data**

Principal Investigators: [name], [name]

Version Date: 6/15/17

Study Title: Isotonic Solutions and Major Adverse Renal Events Trial (SMART)

Institution/Hospital: Vanderbilt University Medical Center

### **Daily Assessments**

Data for each of the following variables will be recorded from ICU admission through 30 days after ICU admission, death, or hospital discharge.

1. Invasive Support:
  - a. Receipt of mechanical ventilation
  - b. Receipt of vasopressors
  
2. Serum Laboratory variables
  - a. Sodium
  - b. Potassium
  - c. Chloride
  - d. Bicarbonate
  - e. Blood urea nitrogen
  - f. Creatinine
  
3. Renal Variables
  - a. Receipt of RRT
  - b. Indications for RRT among patients receiving new RRT
    - i. Oliguria
    - ii. Hyperkalemia with serum potassium > 6.5 mEq/L
    - iii. Acidemia with pH < 7.20
    - iv. Blood urea nitrogen > 70 mg/dL
    - v. Serum creatinine > 3.39 mg/dL
    - vi. Organ edema
    - vii. Other renal failure–related indication
    - viii. Other non–renal failure–related indication
  - c. Plan to continue RRT after discharge

### **Fluid Administration**

1. For each intravenous fluid or blood product order between 24 hours prior to ICU admission and 30 days after ICU admission, the data, time, composition, volume, rate, location, and ordering provider will be collected. Intravenous fluids and blood products for which data will be collected will include:
  - a. 0.9% sodium chloride
  - b. lactated Ringer's
  - c. Plasma-Lyte A®
  - d. 0.45% sodium chloride
  - e. 0.225% sodium chloride
  - f. dextrose in water
  - g. 20% and 5% albumin

Principal Investigators: [name], [name]

Version Date: 6/15/17

Study Title: Isotonic Solutions and Major Adverse Renal Events Trial (SMART)

Institution/Hospital: Vanderbilt University Medical Center

- h. Packed red blood cells
- i. Platelets
- j. Fresh frozen plasma
- k. Semisynthetic colloids

#### **8.4.3 Data at Termination**

1. Date and time of:
  - a. Death
  - b. ICU transfer
  - c. Final ICU discharge
  - d. Hospital discharge
  - e. Cessation of mechanical ventilation
  - f. Cessation of vasopressors
  - g. Cessation of renal replacement therapy

#### **8.5 Outcome Measures**

**Primary Endpoint:** Major Adverse Kidney Events within 30 days. The primary endpoint will be considered present if at least one of the following occur:

- a. A patient dies prior to the earlier of hospital discharge or day 30
- b. A patient receives new renal replacement therapy between enrollment and hospital discharge or day 30
- c. A patient has persistent renal dysfunction at the earlier of hospital discharge or day 30 (persistent renal dysfunction is defined as a final inpatient serum creatinine  $\geq$  200% of baseline)

#### **Secondary Endpoints:**

1. In-hospital mortality before ICU discharge, before 30 days, and before 60 days
2. ICU-free days to day 28
3. Ventilator-free days to day 28
4. Vasopressor-free days to day 28
5. Renal replacement therapy-free days to day 28
6. Incidence of new RRT
7. Duration of new RRT
8. Incidence of persistent renal dysfunction
9. Incidence of Stage II or greater AKI by KDIGO creatinine criteria
10. Highest serum creatinine value
11. Change from baseline to highest serum creatinine value
12. Final serum creatinine value before hospital discharge or 30 days

Principal Investigators: [name], [name]

Version Date: 6/15/17

Study Title: Isotonic Solutions and Major Adverse Renal Events Trial (SMART)

Institution/Hospital: Vanderbilt University Medical Center

13. Serum values for sodium, potassium, chloride, bicarbonate, blood urea nitrogen, and creatinine from enrollment through hospital discharge or 30 days
14. *Urinary biomarkers of pre-renal and intra-renal acute renal failure*
15. *Serum biomarkers of intravascular volume overload and acute renal failure*

